**Table 4. Prednisone Taper Schedule**

Study Week #	Dose (mg/kg, body weight)
0	1.0 qd
2	0.75 qd
4	0.65 qd
6	0.50 qd
8	0.70 qod*
10	0.55 qod
12	0.45 qod
14	0.35 qod
16	0.25 qod
18	0.20 qod
20	0.15 qod
22	0.10 qod
24	0.0

\*qod=every other day. #Timing of steroid taper is defined by when the first dose of prednisone is given.

The prednisone taper should commence by week 2, but it is understood that considerable variation in prednisone taper will occur depending on the subjects' response and other intercurrent illnesses. More rapid tapering of prednisone doses is allowed if clinically appropriate. Rounding of corticosteroid doses is acceptable. Decisions about the use of qod or alternative dosing schedules (eg, Mon/Wed/Fri) may follow institutional practice. Prednisone taper should be completed prior to tapering of other immunosuppressants unless the clinical condition of the subject dictates tapering/discontinuing other medications sooner (eg, toxicity associated with the use of the medication).

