1.4. Sample Size Determination

The study was powered to test the primary endpoint of the study.

The sample size was computed assuming a response rate of 30% at 48 weeks for Arm B (placebo + prednisone). A sample size of 186 randomized subjects provides at least 80% power to detect a 20% difference in the response rates at 48 weeks between the 2 treatment arms at an alpha level of 5% (2-sided).

No replacement of subjects was implemented.

The sample size and power calculations were produced using the software package, East (Cytel Software Corp, Cambridge, MA).

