1.7.2. Randomization Method

Central randomization was implemented in this study. Subjects were randomized based on the following stratification factors:

- Age group (12 to <22 years old vs ≥ 22 years old)
- NIH Global Severity grade (moderate vs. severe)
- Ongoing use of systemic immunosuppressants that were initiated for either treatment of or prophylaxis for acute GVHD (yes vs. no)

Subjects were randomized in a 1:1 ratio to either Treatment Arm A or Treatment Arm B within each randomization stratum. This randomization scheme was implemented within the Interactive Web Response System (IWRS).

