4. EFFICACY

Analysis of efficacy endpoints will be conducted on the ITT population, unless otherwise specified. Table 2 summarizes the efficacy endpoints and analysis methods to be performed. For subgroup and exploratory analyses, the analyses will be performed where appropriate.

An unstratified analysis will be performed for the primary endpoint, because only 8 subjects aged 12 to <22 years were enrolled, which may result in half of the strata with only a few or possibly no subjects randomized to a particular treatment arm. In addition, errors in the assignment of stratification factors into the IWRS for both cGVHD severity and ongoing use of immunosuppressants occurred at the site level in the study.

Table 2. Efficacy Endpoints definition and Analyses

Endpoint	Definition	Analysis Method	Population
Primary Endpoint			
Response Rate at 48 Weeks	
Proportion of responders [complete response (CR) or partial response (PR)] as assessed by investigators at 48 weeks using the NIH Consensus Panel Chronic GVHD Activity Assessment.
 
A subject will NOT be considered as a responder at 48 weeks if he/she meets any of following criteria:
 
 Starts a second line systemic therapy for cGVHD at or prior to the response assessment at 48 weeks Has evidence of progression of the underlying malignancy that was the indication for transplant at or prior to response assessment at 48 weeks Subjects withdrawing from the study or from response assessment prior to 48 weeks. 	
Unstratified Chi-square test
 
Subgroups (from Table 1) Comparison of the treatment arms within each subgroup using p-values from unstratified Chi square test and graph of Odds Ratio (95% CI) for each subgroup.
	
ITT
 
For mITT and Pediatric population, summary or listing will be provided as appropriate

Secondary Endpoints			

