Time to withdrawal of all corticosteroids for treatment of cGVHD	
Time from randomization until the date of complete withdrawal (to 0mg) of corticosteroids used to treat GVHD and sustained for 30 days. Subjects will be considered having a competing risk at the time of death, relapse of the underlying disease, progression of cGVHD, or start of subsequent cGVHD therapy. Subjects with no competing event will be censored at last available study visit.
	
The two Cumulative Incidence Functions (CIFs) of corticosteroid withdrawal will be compared using Gray's Chi square test.
 
Graphs of the CIFs and landmark estimates (95%) at 6 months and 12 months
	ITT

Endpoint	Definition	Analysis Method	Population
		obtained from the CIFs will be provided.	
Time to withdrawal of all ISTs, including corticosteroids for treatment of cGVHD (with the exception of ibrutinib/placebo)	Time from randomization until the date of complete withdrawal (to 0mg) of all corticosteroids used to treat GVHD AND discontinuation of all ISTs sustained for 30 days. Subjects will be considered having a competing risk at the time of death, relapse of the underlying disease, progressive disease (PD) of cGVHD, or start of subsequent cGVHD therapy. Subjects with no competing event will be censored at last available study visit	The two CIFs of withdrawal of all immunosuppressants will be compared using Gray's Chi square test. Graphs of the CIFs and landmark estimates (95%) at 6 months and 12 months obtained from the CIFs will be provided	ITT
Response rate at 24 weeks	
Proportion of responders [complete response (CR) or partial response (PR)] as assessed by investigators at 24 weeks using the NIH Consensus Panel Chronic GVHD Activity Assessment.
 
A subject will NOT be considered as a responder at 24 weeks if he/she meets any of following criteria:
 
 Starts a second line systemic therapy for cGVHD at or prior to the response assessment at 24 weeks Has evidence of progression of the underlying malignancy that was the indication for transplant at or prior to response assessment at 24 weeks 
Subjects withdrawing from the study or from response assessment prior to 24 weeks.
	Comparison of the proportions between the two arms will be performed using Chi-square test	ITT

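### The gated test of time to withdrawal of all immunosuppressants (step 3) is unstratified, although baseline immunosuppressant use is a randomization factor closely tied to the event; this may cost power but does not threaten validity

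*SAP*

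**What the plan says.** SAP section 1.6 tests six endpoints in series at two-sided 0.05. Time to withdrawal of all immunosuppressants is third. Under SAP Table 2 the event occurs when corticosteroids for GVHD have reached 0 mg and every other immunosuppressant has been stopped, sustained for 30 days. Death, relapse, cGVHD progression and new cGVHD therapy are competing events. The test is given as: "The two CIFs of withdrawal of all immunosuppressants will be compared using Gray's Chi square test".

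One of the three randomization factors in SAP section 1.7.2 is "Ongoing use of systemic immunosuppressants that were initiated for either treatment of or prophylaxis for acute GVHD (yes vs. no").

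Protocol section 5.3.2.2.1 schedules prednisone to reach zero at week 24 and says: "Prednisone taper should be completed prior to tapering of other immunosuppressants". The same sentence makes an exception where the subject's clinical condition calls for earlier tapering. Protocol section 6.1.2 also permits the other drugs to be tapered from the start of study treatment.

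SAP section 4 explains the lack of stratification for one endpoint: "An unstratified analysis will be performed for the primary endpoint, because only 8 subjects aged 12 to <22 years were enrolled". It adds that sites made IWRS entry errors in cGVHD severity and in immunosuppressant use. It gives no reason for step 3.

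**The concern.** A subject on no other immunosuppressant at entry can usually have the step-3 event by completing prednisone withdrawal. A new systemic agent for cGVHD would be a competing event, so for this subject step 3 is close to step 2. A subject on another immunosuppressant at entry generally has a further drug to stop, often after prednisone. The two groups may therefore have quite different withdrawal curves.

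Pooling such groups in one test pulls the overall subdistribution hazard ratio towards 1. Because randomization was stratified by this factor, the pooled test also counts between-stratum variation as noise that the design had removed. Both effects lower power. Step 3 has no stated power to draw on: "The study was powered to test the primary endpoint of the study". A failure there ends formal testing of 24-week response, Lee scale improvement and corticosteroid reduction.

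**Working it through.** **The plan's own figure.** SAP section 1.4 says: "The sample size was computed assuming a response rate of 30% at 48 weeks for Arm B (placebo + prednisone"). It continues: "A sample size of 186 randomized subjects provides at least 80% power to detect a 20% difference". With 30% vs 50%, two-sided 0.05, pooled variance and no continuity correction:

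n per arm = [1.96·√(2·0.4·0.6) + 0.8416·√(0.3·0.7 + 0.5·0.5)]² / 0.20² = (1.358 + 0.571)² / 0.04 ≈ 93

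That is 186 in total with 80.0% power (81.5% at the 193 enrolled), so the figure reproduces. It does not concern step 3.

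**Inputs for step 3.** From the documents: 193 subjects, 1:1, two-sided 0.05, and a primary analysis about one year after the last enrolment. Assumed, because the documents are silent:
- share on an immunosuppressant at entry: 30%, 50% or 70%
- subdistribution hazard ratio (HR): 1.8 with 12-month follow-up, or 1.65 with 12 to 30 months
- control-arm 12-month cumulative incidence in each stratum, as in the table below.

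**Model.** Within a stratum, F_A(t) = 1 − (1 − F_B(t))^HR, where A is ibrutinib and B is placebo.

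**Why pooling attenuates.** Take half the subjects on an immunosuppressant and HR 1.8.
- Control incidence 50% (not on) and 15% (on). Proportions without the event in Arm A are 0.50^1.8 = 0.287 and 0.85^1.8 = 0.746, mean 0.517; in Arm B the mean is 0.675. The pooled ratio at 12 months is ln(0.517)/ln(0.675) = 1.68.
- Control incidence 45% and 25%. The Arm A means are (0.341 + 0.596)/2 = 0.468; Arm B is 0.65. The pooled ratio is 1.76.

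**Power.** Monte Carlo, 6,000 trials per setting, allocation balanced within stratum. The test was a log-rank test on the subdistribution risk set, which equals Gray's test when censoring is only administrative. The power columns use half on an immunosuppressant, HR 1.8 and 12-month follow-up. The last column gives the range over all assumed shares and both HR and follow-up settings.

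| Control 12-month incidence, not on / on | Unstratified | Stratified | Stratified, 10% of strata wrong | Gain, all settings |
|---|---|---|---|---|
| 35% / 35% | 77.6% | 77.7% | 77.6% | about 0 |
| 40% / 30% | 76.2% | 76.5% | 76.0% | 0.3 to 0.7 points |
| 45% / 25% | 75.0% | 77.5% | 76.5% | 1.1 to 3.5 points |
| 50% / 15% | 66.9% | 73.4% | 70.5% | 4.8 to 12 points |

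With 10% of strata wrong, the gain over all settings falls to 0.8 to 2.0 points at 45%/25% and 2.5 to 7 points at 50%/15%. A second simulation with the same headline inputs gave about 2 points at a 20-point gap and about 9 at 50%/15%. An extreme 60%/10% split gives 11 to 29 points, but nothing in the documents points to so wide a gap.

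**Hand check of the stratified column.** z = ln(HR)·√(D/4), with D the mean simulated number of events. At 45%/25%, D = 85.3: z = 0.588·4.618 = 2.71, and Φ(2.71 − 1.96) ≈ 77%. At 50%/15%, D = 78.2: z = 0.588·4.422 = 2.60, and Φ(0.64) ≈ 74%. Both agree with the simulation.

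**Type I error.** With HR 1, 50%/15%, half on an immunosuppressant and 12 to 30 months of follow-up, the unstratified test rejects in 3.0% of trials and the stratified test in 4.9%.

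**Limits.** Dropout is not modelled. The Monte Carlo standard error is about 0.6 points per power estimate.

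**The case against.** The strongest reply is that the gap between strata is not fixed by the protocol. The taper order is a recommendation with a clinical exception, earlier tapering is permitted, and the protocol expects considerable variation. The factor is yes/no, so it does not say how many drugs must be stopped. Its wording does not exclude prednisone, so a subject recorded as yes on prednisone alone may have no further drug to stop. All of this stands. A reader might infer that baseline use dictates the number of drugs or the time to withdrawal; the documents do not support that.

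Second, the SAP reports entry errors in this very factor, and the Table 1 subgroup variable refers to GVHD where the randomization factor refers to acute GVHD. That also stands. It argues for a verified value with the randomization wording, not against stratifying. The sparse-cell reason comes from the age factor and does not apply to this factor alone.

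Third, the unstratified test is valid and matches the overall curves and landmarks that Table 2 reports. A reader might infer that the IWRS errors bias it. The trial is double-blind, no error rate is given, and chance imbalance is already allowed for in the test's type I error.

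Fourth, step 3 is tested only after steps 1 and 2 succeed, and step 2 is a component of the step-3 event. The powers above are for step 3 alone; the effect on steps 4 to 6 has not been quantified.

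**Conclusion.** The point holds as one of efficiency. Step 3 leaves out a randomization factor that is closely linked to its event definition, and the SAP gives no reason for this endpoint. The unstratified test does not inflate type I error and is somewhat conservative when strata that were balanced by design differ strongly.

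It is tempting to say that several points of power are lost. That cannot be derived from the documents, which give no share on immunosuppressants, withdrawal rates, effect size or power for step 3. Under the assumptions shown, a gain of about 5 points or more needs a gap nearer 35 than 20 percentage points between strata. Such a gap is plausible given the recommended taper order, but it is not established. With no gap, stratifying costs essentially nothing.

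**What to change.** Before unblinding, amend the SAP Table 2 row for time to withdrawal of all immunosuppressants:
- Make the gated test a Gray's test stratified by ongoing systemic immunosuppressant use at enrolment (yes/no).
- Take the stratum from verified clinical-database data, with the same acute GVHD wording as the randomization factor.
- Keep the unstratified Gray's test as a sensitivity analysis.
- Show the cumulative incidence curves and the 6- and 12-month landmarks within each stratum as well as overall.

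If the sponsor prefers the unstratified test, the SAP should say why the primary-endpoint reasoning extends to step 3.

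The cost is a few lines of SAP text, verification of one baseline variable, and a strata option in the analysis. The small downside is that the analysis stratum is the verified value and will differ from the IWRS value for subjects entered wrongly.

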### **2.2. Secondary Objective(s)**

- To compare the two treatment arms in terms of the following:

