#### **Efficacy**

- Response rate at 24 weeks (the proportion of responders [CR or PR]) as defined by the NIH Consensus Development Project (2014)
- Duration of response (DOR)
- Proportion of subjects obtaining a steroid dose level less than 0.15 mg/kg/d at 24 weeks
- Time to withdrawal of all immunosuppressants (with the exception of ibrutinib/placebo)
- Overall survival (OS)
- Lee cGVHD symptom scale improvement

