#### **10.4.2. Secondary Endpoints for Efficacy**

The secondary efficacy endpoints are:

- Response rate at 24 weeks (the proportion of responders [CR or PR]) as defined by the NIH Consensus Development Project (2014)
- Duration of response (DOR) will be defined from the time of initial partial or complete response until progression of cGVHD
- Proportion of subjects with steroid dose reduction to a level of less than 0.15 mg/kg/d at 24 weeks
- Time to withdrawal of all immunosuppressants (with the exception of ibrutinib/placebo)

- Overall survival (OS) is defined as the time from randomization until death due to any cause
- Improvement in Lee cGVHD Symptom Scale scores will be compared between the two treatment arms

Proportion of subjects with improvement in overall score on the Lee cGVHD Symptom Scale and the proportion of subjects with steroid dose reduction will be analyzed using the same method for the primary efficacy endpoint. The Kaplan Meier methodology will be used to estimate the distribution of OS for each treatment group. The log-rank test will be used to compare the OS between the 2 treatment arms. Time to withdrawal of all immunosuppressants will be analyzed using the same method used for OS.

Duration of response is defined as the interval between the date of initial documentation of a response (PR or better), and the date of first documented evidence of progressive cGVHD or death for responders only. Responders will include subjects who achieve response (PR or better) based on NIH 2014 cGVHD criteria. Non-responders will be excluded from the analysis for DOR. Median duration of response will be estimated using Kaplan Meier methodology.

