2. GENERAL ANALYSIS CONSIDERATION

2.1. Analysis Sets

2.1.1. Intent-to-Treat Population (ITT)

The intent-to-treat (ITT) population includes all randomized subjects. Subjects in the ITT population will be analyzed according to the treatment to which they were randomized. The ITT population will be the primary population for the analyses of efficacy endpoints (except for duration of response), all baseline characteristics, and patient reported outcome (PRO) endpoints.

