Improvement in overall score on Lee cGVHD Symptom Scale	
Proportion of subjects who had Lee total score decreasing at least 7 points at 2 consecutive visits with no PD, relapse of underlying disease or start of subsequent cGVHD treatment.
 
Proportion of subjects who had Lee total score decreasing at least 7 points at any time during the study (not preceded by PD, relapse of underlying disease or start of subsequent cGVHD treatment)
	
Comparison of the proportions between the two arms will be performed using chi-square test.
 
Supportive: Summary of the proportions of subjects with at least 7 points improvement at any
	ITT

Endpoint	Definition	Analysis Method	Population
	Mean Lee scores overtime	time will be provided. Summary of mean Lee scores overtime and graphs by treatment arm will be provided	
Proportion of subjects who achieve reduction of corticosteroids dose level to less than 0.15 mg/kg/d at 24 weeks sustained for at least 30 days	Proportion of subjects with prednisone equivalent dose reduction to a level of less than 0.15 mg/kg/d for a duration of at least 30 days at 24 weeks Mean daily corticosteroid dosing overtime	Comparison of the proportions between the two arms will be performed using Chi-square test Supportive: Mean (95%CI) of daily corticosteroid dosing over time will be summarized and plotted by arm	ITT
Duration of response	The interval between the date of initial documentation of a response (PR or better), and the date of first documented evidence of progressive cGVHD, relapse of underlying disease, start of subsequent cGVHD treatment, or death for responders only.	DOR will be estimated by Kaplan-Meier methodology: median DOR and landmark estimates with 2-sided 95% CIs will be provided for each treatment arm. K-M plots will be provided	Responders include subjects with response at any time during study treatment
Overall Survival	Time from the date of randomization until the date of death due to any cause. All deaths observed at the time of the data extraction date will be considered as events. For subjects who were not known to have died at the time of the analysis, OS data will be censored at date last known alive.	Survival will be estimated by Kaplan-Meier methodology: median OS and landmark estimates with 2-sided 95% CIs will be provided for each treatment arm. Kaplan-Meier plots will be provided	ITT
Exploratory Endpoints			

Endpoint	Definition	Analysis Method	Population

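### Duration of response is listed for comparison between arms but analysed only within each arm's responders, so the side-by-side medians are not a randomized comparison and can mislead in either direction

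*SAP*

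**What the plan says.** Protocol 2.2 introduces the secondary objectives with "To compare the two treatment arms in terms of the following" and includes DOR in the efficacy list. Protocol 10.1.1 assigns all efficacy analyses to the ITT population, but Protocol 10.4.2 states for this endpoint: "Non-responders will be excluded from the analysis for DOR".

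SAP 2.1.1 names DOR as the one exception to ITT. SAP Table 2 (section 4) sets the population: "Responders include subjects with response at any time during study treatment". The clock runs from first response to "progressive cGVHD, relapse of underlying disease, start of subsequent cGVHD treatment, or death for responders only". The planned output is "median DOR and landmark estimates with 2-sided 95% CIs will be provided for each treatment arm", plus plots. No test, hazard ratio or difference between arms is specified.

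SAP 1.6 leaves DOR out of the six-step testing hierarchy and gives it the role of supporting the response endpoints. Neither document plans a measure of time in response over all randomized subjects.

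**The concern.** Randomization balances the arms, not the responders within them. The trial is designed around a difference in response: 30% on placebo and 20 points more on ibrutinib at Week 48 (Protocol 10.2, SAP 1.4). If that difference is real, Arm A's DOR set contains people who would not have responded on placebo, and Arm B's set has no counterpart to them. The difference between the two medians then mixes any effect on durability with a difference in who was counted.

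The distortion has no fixed sign. If the added responders lose response sooner, ibrutinib looks less durable even though nobody lost response time. If they keep it longer, ibrutinib looks more durable even though common responders gained nothing. In either case the table does not answer the objective in Protocol 2.2, and it is an unreliable support for the response endpoints.

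**Working it through.** **The plan's own figure.** The documents give no figure for DOR. The sample size reproduces. With p = 0.30 and 0.50, pooled proportion 0.40, two-sided 5% and 80% power:

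n per arm = [1.960·√(2·0.40·0.60) + 0.842·√(0.30·0.70 + 0.50·0.50)]² / 0.20² = 93, so 186 in total with power 0.800. The DOR issue does not affect this.

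**Inputs for the illustration**

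- From the documents: 30% vs 50% in response at Week 48. The first response visit is Week 5 Day 1, which is 4 weeks after start, so onset is set at Week 4. That leaves 44 weeks, or 10.12 months, to Week 48.
- Assumed, because the documents give no durations and no ever-response rates: exponential duration; every subject who would respond on placebo also responds on ibrutinib, with the same median m in both arms (common responders); added responders respond only on ibrutinib, with median f·m; being in response at Week 48 means that response has not yet ended.

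**Step 1: ever-response rates that give 30% vs 50% at Week 48.** Let S(t; m) = 2^(−t/m). For m = 24 and f = 0.5:

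- S(10.12; 24) = 0.747 and S(10.12; 12) = 0.557.
- Common responders: 0.30 / 0.747 = 0.402.
- Added responders: 0.20 / 0.557 = 0.359.
- Ever-response: about 40% on placebo and 0.402 + 0.359 = 76% on ibrutinib.
- Added share of Arm A's DOR set: 0.359 / 0.761 = 47%.

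**Step 2: responder-only medians.** Placebo: 24.0 months. For ibrutinib, solve 0.528·2^(−t/24) + 0.472·2^(−t/12) = 0.5. With x = 2^(−t/24), this is 0.472x² + 0.528x − 0.5 = 0, so x = 0.612 and t = 17.0 months.

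**Step 3: mean time in response to Week 48, all randomized.** Per responder this is (median / ln 2)·(1 − S(10.12)): 8.77 months for common responders and 7.66 for added ones.

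- Placebo: 0.402 × 8.77 = 3.53 months.
- Ibrutinib: 3.53 + 0.359 × 7.66 = 6.28 months.
- Ratio: 6.28 / 3.53 = 1.78.

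**Step 4: range.** The same steps with other assumed durations:

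| Common median m (months) | Added median ÷ m | Ever-response, placebo vs ibrutinib | Responder-only median, placebo vs ibrutinib | Ratio of mean time in response |
|---|---|---|---|---|
| 18 | 0.5 | 44% vs 88% | 18.0 vs 12.5 | 1.83 |
| 24 | 0.5 | 40% vs 76% | 24.0 vs 17.0 | 1.78 |
| 24 | 0.75 | 40% vs 70% | 24.0 vs 21.2 | 1.70 |
| 24 | 1 | 40% vs 67% | 24.0 vs 24.0 | 1.67 |
| 24 | 1.5 | 40% vs 65% | 24.0 vs 27.8 | 1.63 |
| 24 | 2 | 40% vs 63% | 24.0 vs 30.3 | 1.62 |
| 36 | 0.5 | 36% vs 66% | 36.0 vs 26.0 | 1.74 |

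Common responders do equally well in both arms in every row. The difference between medians still runs from clearly negative through zero to clearly positive, while the all-randomized measure favours ibrutinib throughout.

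**The case against.** The strongest reply is that the plan makes no DOR comparison. Table 2 gives estimates for each arm without a contrast. Protocol 10.4.2 likewise plans only a Kaplan-Meier median for DOR, while naming a log-rank test for survival. SAP section 1 says its definitions and methods supersede the protocol's, and responder-only DOR is the definition in both documents. Lasting benefit is already examined in ITT: response at Weeks 24 and 48 counts second-line therapy, malignancy progression and withdrawal as non-response, and withdrawal of corticosteroids and of all immunosuppressants is analysed with competing risks.

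Much of this stands. No formal inference is at risk, and the problem is confined to how a descriptive table will be read. But the SAP keeps DOR as a secondary endpoint, section 6 records no change to it, and Table 2 does not say that the two medians are not a treatment comparison. The Week 24 and Week 48 rates are snapshots and do not measure how long response lasted.

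It is also fair that a ratio of mean times mostly carries the difference in response rates: with equal durations it is 0.50/0.30 = 1.67. The measure combines frequency and duration over all randomized subjects. It does not isolate durability.

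A reader might go further and infer that the DOR table will favour placebo if ibrutinib works. The documents do not support that. Nothing in them says whether added responders have shorter or longer responses.

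A reader might also insert 30% and 50% directly as ever-response rates. They are rates at Week 48. With a 12-month common median and added responders at half of it, that shortcut implies only 0.30 × 0.557 = 17% vs 17% + 0.20 × 0.311 = 23% in response at Week 48. Recovering 30% vs 50% would need ever-response of 0.30/0.557 = 54% vs 54% + 0.20/0.311 = 118%, which is impossible.

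**Conclusion.** The concern holds as a mismatch between objective and analysis: an outcome listed for comparison between arms is estimated only in post-randomization subsets, with no all-randomized counterpart. In the central illustration the responder-only medians differ by 7 months against ibrutinib (24.0 vs about 17.0) while time in response per randomized subject is about 1.8 times higher on ibrutinib. With longer responses among added responders the medians differ in the other direction, and with equal durations the distortion vanishes. These sizes rest on assumed exponential durations, a common onset, the chosen medians, and no effect of ibrutinib on common responders. They show what is possible and are not a forecast.

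The consequence is limited. DOR is descriptive, outside the hierarchy and carries no alpha. The primary test, the sample size and the type I error are untouched. This is an inexpensive improvement to a supportive analysis.

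**What to change.** In the DOR row of SAP Table 2:

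1. Keep the responder-only Kaplan-Meier estimates, labelled as descriptive within arm and not a treatment comparison.
2. Add a supportive ITT analysis: mean time in response (CR or PR) from randomization to Week 48, with never-responders scored 0.
3. End time in response at the first evaluable assessment that is no longer CR or PR, or at an existing DOR event, whichever comes first. Using the DOR events alone would leave a subject who falls from PR to stable disease counted as in response. Treat flare assessments as inevaluable, as Protocol Appendix I does.
4. Report the difference between arms with a 95% CI, for example by bootstrap. Repeat it over a longer horizon at the final analysis, about two years after the last enrolment (SAP 1.5.3).
5. Base any between-arm statement about duration on this estimate.

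The cost is a short addition to the SAP and one extra supportive table. It needs no new data and no alpha. Its main weakness is that response timing is known only to the assessment visits (Weeks 5, 13, 25, 37 and 49).
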